4.2 SAFETY ANALYSES

Safety data will be assessed through descriptive summaries using the OLE population. All data available up until the clinical cut-off date (CCOD) will be reported

Safety evaluations for the OLE population will include data from the first dose of treatment in Part 1 until the patient completes/withdraws from the Part 1 (OLE) of the study GA28951, this includes any 12-week safety follow-up data.

4.2.1 Extent of Exposure

Exposure to study treatment will be summarized by:

- treatment duration (weeks)
- number of patients receiving a dose at each visit
- number of doses received/missed for a patient

4.2.2 Adverse Events

Verbatim descriptions of AEs will be mapped to the latest version of the Medical Dictionary for Regulatory Activities (MedDRA).

Adverse events (AEs) will include all terms recorded on the AE Case Report Form (CRF) pages (except pregnancies). For each recorded AE, the term entered by the investigator describing the event (the “reported term”) will be assigned a standardized term (the “preferred term”) and assigned to a superclass term on the basis of the Medical Dictionary for Regulatory Activities (MedDRA) World Health Organization (WHO) dictionary of terms. All analyses of AE data will be performed using the preferred terms and system organ class unless otherwise specified.

For the etrolizumab program, the adverse events of special interest (AESIs) are the following:

- Systemic hypersensitivity reactions and anaphylactic and anaphylactoid reaction which will be reported using the MedDRA anaphylactic reaction Standard MedDRA Query (SMQ) algorithmic and Hypersensitivity SMQ narrow.
- Neurological signs, symptoms, and AEs that may suggest possible progressive multifocal leukoencephalopathy (see Appendices 5 and 6 of Protocol)
- Suspected transmission of an infectious agent by the study drug
- Cases of potential drug-induced liver injury that include an elevated alanine aminotransferase (ALT) or aspartate aminotransferase (AST) in combination with either an elevated bilirubin or clinical jaundice, as defined by Hy's Law

Specific AEs listed below will also be reported:

- Serious infections
- Gastrointestinal Infections
- Opportunistic infections
- Malignancies
- Injection site reactions

A listing or summary table (e.g., $n > 10$) of all AEs suspected or confirmed, and AEs associated with COVID-19 will be generated. Associated AEs are defined as all AEs reported within a time window of 7 days prior and 30 days after the confirmed COVID-19 start date (dates inclusive). Additionally, a listing of patients experiencing 'long COVID-19' will be generated. This listing will include all AEs with a duration >30 days occurring after a confirmed COVID-19 infection or a positive PCR test.

All AESIs and specific AEs will be determined using a selection of eCRF tick box or MedDRA SMQs, Adverse Events Group Terms (AEGTs), High Level Term (HLTs), High Level Group Terms (HLGTs), System Organ Class (SOC), as appropriate.

Summary tables will be generated for AEs, serious adverse events (SAEs), deaths, AEs leading to discontinuation of study drug, and AESIs. A listing will be generated for AEs, deaths, selected AESIs/specific AEs, and COVID-19 AEs. Pregnancies will be reported as narratives in the study CSR.

Summary tables of AEs will summarize the incidence of treatment-emergent AEs only. Treatment-emergent events are defined as any new AE reported on or after the first dose of OLE study drug or any worsening of an existing condition. Note that worsening of existing conditions include AEs ongoing from the UC parent studies (GA28948, GA28949, GA28950, GA29102, and GA29103). Otherwise, only AEs reported on or after the first dose of OLE study drug are included. If the onset date of the AE is prior to

the day of first dose, the AE will be considered treatment emergent only if the most extreme intensity is greater than the initial intensity (i.e., the intensity for a given AE increases and its end date is on or after the date of the first dose). For all summary tables, the AEs will be sorted by SOC (in decreasing order of overall incidence) and then by preferred term (PT) (in decreasing order of overall incidence).

For OLE etrolizumab treatment, the incidence count for each AE PT will be defined as the number of patients reporting at least one treatment-emergent occurrence of the event (multiple occurrences of the same AE in 1 patient will be counted only once). The proportion of patients with an AE will be calculated as the incidence count divided by the total number of patients in the population. Each table will also present the total number of AEs reported where multiple occurrences of the same AE in an individual are counted separately.

Rate tables will be generated for selected AEs of interest. The rate per 100 patient years and 95% CIs will be summarized by treatment group and will be calculated by:

$$\begin{aligned} & \text{AE Rate (per 100 patient years)} \\ &= \frac{\text{Total number of AEs (in OLE only)}}{\text{Total number of patient years at risk (in OLE only)}} \times 100 \end{aligned}$$

where the total patient-years at risk is the sum over all patients of the time intervals (in years) from the first dose of study treatment in Part 1 (OLE) until the patient completes/withdraws from the study (including the 12-week safety follow-up, if applicable). Only treatment emergent AEs with an onset date after the first dose of open label etrolizumab in GA28951 will be included within these outputs.

All summary tables and listings will report AEs using the OLE population.

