5.3.3 Adverse Events of Special Interest (Immediately Reportable to the Sponsor)

Adverse events of special interest are required to be reported by the investigator to the Sponsor immediately (i.e., no more than 24 hours after learning of the event; see Section 5.5.2 for reporting instructions). Adverse events of special interest for this study include the following:

- Cases of potential drug-induced liver injury that include an elevated ALT or AST in combination with either an elevated bilirubin or clinical jaundice, as defined by Hy's law (see Section 5.4.6.6)

- Suspected transmission of an infectious agent by etrolizumab as defined below:

Any organism, virus, or infectious particle (e.g., prion protein transmitting transmissible spongiform encephalopathy), pathogenic or non-pathogenic, is considered an infectious agent. A transmission of an infectious agent may be suspected from clinical symptoms or laboratory findings that indicate an infection in a patient exposed to a medicinal product. This term applies only when a contamination of the study drug is suspected.

- Adverse events of special interest specific to etrolizumab:

Systemic hypersensitivity reactions and anaphylactic and anaphylactoid reactions (see Section 5.1.1.2 and Sampson's Criteria in Appendix 9)

Neurological signs, symptoms, and adverse events that may suggest possible PML on the basis of a positive finding on the PML Subjective Checklist that is accompanied by a positive finding on the PML Objective Checklist or if there is strong clinical suspicion for PML (see Appendix 7 PML algorithm and Section 5.1.1.1.1, above)

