6.3.1 Adverse Events

Verbatim descriptions of treatment-emergent adverse events will be coded and their incidence and observation time-adjusted rate will be summarized, as appropriate. A treatment-emergent adverse event is defined as any new adverse event reported or any worsening of an existing condition on or after the first dose of study drug. In addition, separate summaries will be generated for serious adverse events, deaths, and adverse events leading to discontinuation of etrolizumab. Adverse events will be summarized by mapped term, appropriate thesaurus level, and toxicity grade.

Analyses will be performed for:

- Systemic hypersensitivity events
Specific analyses will be performed for anaphylactic reactions with use of the anaphylactic reaction Sampson's criteria (see [Appendix 9](#)).
- Serious infections, in particular GI infections
- Opportunistic infections
- Malignancies
- Injection-site reactions

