Appendix 8 Patient Daily Diary

PATIENT DIARY CARD
FORMAT MAY CHANGE DURING THE SWITCH TO ELECTRONIC FORMAT

PATIENT NUMBER

Monthly Record of Study Medication Injections
--

Week	Date/Time of Injection dd-mmm-yyyy e.g. 30/Sep/2013 (24 h clock) e.g. 14:00	Location of Injection	Information About Your Injection
0 Day 1	INJECTION 1 Date: ___/___/_____ Time: ___:___  Injection done at clinic  Injection administered by caregiver	 thigh  arm  abdomen	 Injection not done  Less than full amount of pre-filled syringe injected  Incorrectly injected medication*  OTHER COMMENTS:
4	INJECTION 2 Date: ___/___/_____ Time: ___:___  Injection done at clinic  Injection administered by caregiver	 thigh  arm  abdomen	 Injection not done  Less than full amount of pre-filled syringe injected  Incorrectly injected medication*  OTHER COMMENTS

An incorrectly administered injection is defined as

- an SC injection which was given intramuscularly
- an SC injection was given to a body site that is not allowed per protocol (namely a site other than thigh, arm or abdomen)

If you experience any side effects following your injection please remember to describe these to the study staff the next time you speak with them

RESULT OF PREGNANCY TEST
 DATE PREGNANCY TEST CONDUCTED --/--/----
 PREGNANCY TEST RESULT: POSITIVE NEGATIVE NOT DONE

Appendix 9

Clinical Criteria for Diagnosing Anaphylaxis

These criteria are taken from a summary report from the second symposium on the definition and management of anaphylaxis, conducted by the National Institute of Allergy and Infectious Disease/Food Allergy and Anaphylaxis Network.¹ Anaphylaxis is highly likely when any one of the following three criteria is fulfilled:

1. Acute onset of an illness (minutes to several hours) with involvement of the skin, mucosal tissue, or both (e.g., generalized hives, pruritus or flushing, swollen lips-tongue-uvula)

AND AT LEAST ONE OF THE FOLLOWING:

- Respiratory compromise (e.g., dyspnea, wheeze-bronchospasm, stridor, reduced peak expiratory flow, hypoxemia)

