4.4 CHANGES TO PROTOCOL-PLANNED ANALYSES

The incidence of ATAs to etrolizumab was extensively evaluated in the Ulcerative Colitis and Crohn's Disease within the phase 3 program where, no obvious impact on injection site reactions or other relevant safety parameters such as hypersensitivity was found. Following this evaluation ATAs has been de-prioritised from a safety objective and outcome measure in GA28951 to an exploratory objective and outcome measure.

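### The protocol plans the anaphylaxis analysis on the Appendix 9 clinical criteria; the SAP names MedDRA queries instead and does not list this among its changes

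*SAP*

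**What the plan says.** **Protocol.** Under systemic hypersensitivity events, Section 6.3.1 states: "Specific analyses will be performed for anaphylactic reactions with use of the anaphylactic reaction Sampson's criteria", with a pointer to Appendix 9. Section 5.3.3 defines the AESI by the same reference: "Systemic hypersensitivity reactions and anaphylactic and anaphylactoid reactions (see Section 5.1.1.2 and Sampson's Criteria in Appendix 9". Section 5.1.1.2 also sends the reader to Appendix 9. The appendix is a clinical definition: "Anaphylaxis is highly likely when any one of the following three criteria is fulfilled".

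**SAP.** Section 4.2.2 lists systemic hypersensitivity, anaphylactic and anaphylactoid reactions as an AESI, to be reported by the anaphylactic reaction "Standard MedDRA Query (SMQ) algorithmic and Hypersensitivity SMQ narrow". Later in the same section comes a general rule: "All AESIs and specific AEs will be determined using a selection of eCRF tick box or MedDRA SMQs", followed by other MedDRA groupings, each to be used as appropriate. The SAP text available for review mentions neither Appendix 9 nor the clinical criteria.

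**Precedence and changes.** SAP Section 1 says that the SAP's analyses replace the protocol's for reporting, and that changes to planned analyses are described in Section 4.4. Section 4.4 contains one item, which begins "The incidence of ATAs to etrolizumab was extensively evaluated" and explains why ATAs were moved to exploratory status. Section 5 says there is no supporting document.

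**The concern.** The protocol fixed how an anaphylaxis case would be recognised for analysis. The SAP, which governs the report, identifies cases by a different route, and a reader who relies on Section 4.4 would not learn this.

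Incidence and severity of hypersensitivity reactions is a stated safety objective and outcome in both documents, and anaphylaxis is the component for which the protocol asked for its own analysis. Protocol 5.1.1.2 reports no anaphylactic reaction in the completed Phase I/II trials, so a low count is plausible here too, and a low count is sensitive to who is classed as a case. Followed as written, the SAP would produce an anaphylaxis figure that a reader of the protocol could take to be the Appendix 9 figure when it is not.

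**Working it through.** No arithmetic decides this point. The check is a comparison of the provisions.

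1. **Planned definition.** Protocol 6.3.1 names Appendix 9 for the anaphylaxis analysis, and 5.3.3 names it for the AESI. Appendix 9 is met by any one of three sets of findings:
   - Set 1: acute onset of illness over minutes to several hours with skin or mucosal involvement, plus respiratory compromise or reduced blood pressure (or its associated symptoms).
   - Set 2: two or more of four kinds of finding soon after exposure to a likely allergen.
   - Set 3: reduced blood pressure after exposure to a known allergen; in adults, systolic below 90 mmHg or a fall of more than 30%.

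   All three are judged on the clinical course of the case.

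2. **SAP definition.** The sentence in SAP 4.2.2 specific to this AESI names two MedDRA queries and nothing else.

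3. **Is Appendix 9 kept by another route?** The general clause allows a tick box. An investigator who flags an AESI works under a protocol definition that cites Appendix 9, so some link may survive. But the clause offers a choice of sources, does not say which applies to anaphylaxis, and includes no step in which a case is classified against the criteria.

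4. **Do coded terms carry the needed information?** Protocol 5.4.6.1 asks sites to record a diagnosis, where known, in place of individual signs and symptoms. A coded term by itself may therefore not show whether Appendix 9 was met. Under Protocol 5.5.2, AESI reports carry the case details available within 24 hours, and these are what a classification would use.

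5. **Was a change declared?** SAP Section 1 points to 4.4, 4.4 covers ATAs only, and Section 5 rules out a further document.

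6. **Does the shortened report explain it?** No. SAP Section 4 limits efficacy reporting because the report is synoptic, but says all safety outcome measures will be reported.

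7. **Was the whole AESI list rewritten this way?** No. In the same list, the item on possible progressive multifocal leukoencephalopathy still refers to protocol appendices and the liver item still uses Hy's law. The anaphylaxis item lost its link to the protocol criteria.

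**Scale, as illustration only.** Assume that between 1000 patients (an assumed figure) and the maximum of 2100 are dosed in Part 1. One case more or fewer then moves the reported proportion by between 1/2100 = 0.05% and 1/1000 = 0.10%. How many cases the two definitions would classify differently is not known.

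**The case against.** The strongest reply is that the SAP supersedes the protocol, the rule in force is therefore clear, and the study is single-arm and descriptive with no tests, so little depends on the choice. Declaring and justifying the queries in Section 4.4 would by itself remove the inconsistency. Much of this stands. It is not unclear which document governs, and no inference is at risk. But precedence makes the missing declaration matter more, since Section 4.4 is where a reader is told to look.

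A second reply is that the tick-box clause may keep investigator-identified cases in the count. That is possible, and it weakens any claim that cases would be lost. It does not amount to a commitment to Appendix 9.

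A reader might also infer that the queries would sweep in unrelated skin or respiratory events, or miss true cases coded under other terms. The documents do not support this: they give neither the content nor the logic of the queries, and the SAP specifies the algorithmic form of the anaphylaxis query. Nor should Appendix 9 be read as always requiring timing relative to an injection or a blood pressure threshold. Set 1 sets no timing relative to injection, the adult thresholds belong to set 3 alone, and sets 1 and 2 can be met without a fall in pressure.

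**Conclusion.** The point holds as an undeclared change of case definition for one protocol-specified analysis. It should be corrected before reporting, because followed as written the SAP drops the Appendix 9 analysis and may change a rare-event safety count.

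Its size is bounded by what the documents can show. There is no anaphylaxis count or rate for this study, so neither the magnitude nor the direction of any difference between the two counts can be stated. A claim that the count would change several-fold would have no basis.

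Two further readings go too far. One is that a key safety outcome has been redefined. The listed outcome is hypersensitivity reactions as a whole, for which Protocol 6.3.1 sets no Appendix 9 rule; the change affects the anaphylaxis analysis within it. The other is that results would no longer match the parent studies. The documents do not say how those studies counted anaphylaxis, and SAP 4.2.2 presents its AESI list as one for the whole etrolizumab programme.

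The conclusion rests on the SAP text supplied and on reading the AESI-specific sentence as the operative rule over the general clause.

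**What to change.** In SAP 4.2.2, keep the two queries as the search step. Add that every case they retrieve, and every anaphylaxis or systemic hypersensitivity AESI reported by an investigator, is classified against Appendix 9 as met, not met or unclassifiable for lack of clinical data. Present the Appendix 9 count next to the query count. In SAP 4.4, record that the query definition has been added to the one planned in the protocol, and why.

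At minimum, if the Appendix 9 analysis is not restored, declare and justify the substitution in 4.4. That resolves the documentation but not the loss of the planned analysis.

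The cost is a medical review of what is likely to be a small number of cases, plus a few sentences. The documents do not promise narratives for Part 1 AESIs, so the review should not be costed as if narratives already exist. Some cases, for example after home dosing, may lack the blood pressure or timing data needed. The unclassifiable category keeps these visible so that they are not forced into either count.

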4.4.1.1 Physical Examinations

A partial physical examination will be performed at Day 1 of the OLE-SM study and recorded as “normal” or “abnormal” at the times indicated in the Schedule of Assessments. New or worsened clinically significant abnormalities should be recorded as adverse events on the Adverse Event eCRF. Past resolved adverse events will be recorded in the medical history according to their medical relevance. Adverse events reported as ongoing at the end of the parent study (i.e., the Phase II OLE study or a Phase III controlled study) will be stated as unresolved in those studies and reopened in Study GA28951. The adverse event will be reported in Study GA28951 with the start date and adverse event term identical to those in the Phase II OLE study or the Phase III controlled study. The adverse event severity (National Cancer Institute Common Terminology Criteria for Adverse Events [NCI CTCAE] grade) should be evaluated by the investigator at the start of Part I (OLE) and recorded in the "AE initial NCI CTCAE grade" field of the Adverse Event eCRF for Study GA28951. The most extreme NCI CTCAE grade for the event should also be recorded, taking into account the severity of the event since it was first reported during the parent study.

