5.4 METHODS AND TIMING FOR CAPTURING AND ASSESSING SAFETY PARAMETERS

5.4.1 Adverse Event Reporting Period for Part 1 (OLE)

After informed consent has been obtained, all adverse events, regardless of relationship to study drug, will be reported until the patient completes Part 1 (OLE).

During Part 1 (OLE), the investigator is responsible for ensuring that all adverse events (see Section 5.3.1 for definition) are recorded on the Adverse Event eCRF and reported to the Sponsor in accordance with instructions provided in this section and in Sections 5.5, 5.6, and 5.7. The investigator is also responsible for reporting medical device complaints (see Section 4.3.3.3).

For each adverse event recorded on the Adverse Event eCRF, the investigator will make an assessment of seriousness (see Section 5.3.2 for seriousness criteria), severity (see Section 5.4.4), and causality (see Section 5.4.5).

Investigators will seek information on adverse events at each patient contact. All adverse events, whether reported by the patient or noted by study personnel, will be recorded in the patient's medical record and on the Adverse Event eCRF. Past resolved adverse events will be recorded in the medical history according to their medical relevance. Adverse events reported ongoing at the end of the Phase II OLE or Phase III controlled studies will be stated unresolved in those studies and reopened in Study GA28951. The adverse event will be reported in Study GA28951 with the start date and adverse event term identical to those in the parent study (i.e., the Phase II OLE study or a Phase III controlled study). The severity (NCI CTCAE grade) should be evaluated by the investigator at the start of Part I (OLE) and recorded in the "AE initial NCI CTCAE grade" field of the Adverse Event eCRF for Study GA28951. The most extreme NCI CTCAE grade for the event should also be recorded, taking into account the severity of the event since it was first reported during the parent study.

Adverse events reported as ongoing at the end of Part 1 (OLE) (i.e., the end of the 12-week safety follow-up) will be recorded as unresolved.

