5.4.6.3 Persistent or Recurrent Adverse Events

A persistent adverse event is one that extends continuously, without resolution, between patient evaluation timepoints. Such events should only be recorded once on the Adverse Event eCRF. The initial severity (NCI CTCAE grade) of the event should be recorded at the time the event is first reported during Study GA28951. If a persistent adverse event becomes more severe, the most extreme NCI CTCAE grade should also be recorded on the Adverse Event eCRF. For adverse events reported as ongoing at the end of a parent study (i.e., the Phase II OLE study or a Phase III controlled study), the severity (NCI CTCAE grade) should be evaluated by the investigator at the start of Part 1 (OLE) and recorded in the "AE initial NCI CTCAE grade" field of the Adverse Event eCRF for Study GA28951. The most extreme NCI CTCAE grade for the event should also be recorded, taking into account the severity of the event since it was first reported during the parent study.

If the event becomes serious, it should be reported to the Sponsor immediately (i.e., no more than 24 hours after learning that the event became serious; see Section 5.5.2 reporting instructions). The Adverse Event eCRF should be updated by changing the event from "non-serious" to "serious," providing the date that the event became serious, and completing all data fields related to serious adverse events.

A recurrent adverse event is one that resolves between patient evaluation timepoints and subsequently recurs. Each recurrence of an adverse event should be recorded separately on the Adverse Event eCRF.

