3. ANALYSIS SETS

The analysis population for the purposes of analyses are presented in below:

Table 2 Analysis Populations

Open-Label Extension	Patients who receive at least one dose of study drug in Study GA28951 Part 1 OLE
	Timeframe is from first dose of study drug in the GA28951 Part 1 (OLE) to the patient's last visit in GA28951 Part 1 (OLE), or safety follow-up, whichever is latest. Summaries will primarily focus on safety events arising after first dose of study drug in Study GA28951 Part 1 (OLE).

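### For adverse events carried over from a parent study, the SAP's treatment-emergent rule does not require the worsening to occur in the OLE

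*SAP*

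**What the plan says.** **How carried-over events are recorded.** Protocol 4.4.1.1 has an event that is ongoing at the end of the parent study reopened in GA28951 "with the start date and adverse event term identical to those in the Phase II OLE study or the Phase III controlled study". Its onset therefore always precedes the first OLE dose. Two grades are then entered:

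- The initial grade is fixed at rollover. Under Protocol 5.4.6.3, "the severity (NCI CTCAE grade) should be evaluated by the investigator at the start of Part 1 (OLE") and entered in the initial-grade field.
- The most extreme grade is recorded "taking into account the severity of the event since it was first reported during the parent study" (Protocol 5.4.1). The same instruction appears in 4.4.1.1 and 5.4.6.3.

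**How they are classified.** Protocol 6.3.1 counts as treatment emergent a new event or "any worsening of an existing condition on or after the first dose of study drug". SAP 4.2.2 defines the term as "any new AE reported on or after the first dose of OLE study drug or any worsening of an existing condition", which attaches the timing to new events only. For events with onset before the first OLE dose it adds that "the AE will be considered treatment emergent only if the most extreme intensity is greater than the initial intensity". It explains this as an increase in intensity with an end date on or after the first dose.

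**Which parent studies are named.** SAP 4.2.2 says that worsening of existing conditions covers events ongoing from GA28948, GA28949, GA28950, GA29102 and GA29103. It then limits everything else to events reported from the first OLE dose onward. GA27927 is not in the list.

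**The concern.** The two grades being compared cover different periods. The initial grade starts the clock at OLE entry, while the most extreme grade looks back to the first report in the parent study. A difference between them can mean that the event worsened in the OLE, or that it had improved before the patient entered.

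Long-term safety is an objective of Part 1, and incidence and severity of adverse events is the first safety outcome listed in both documents. Summary tables in SAP 4.2.2 are restricted to treatment-emergent events, so a wrong flag goes straight into them. A patient who also has a new event of the same preferred term is already in the patient count. The event total still rises, because "Each table will also present the total number of AEs reported where multiple occurrences of the same AE in an individual are counted separately".

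**Working it through.** The plan gives no figure to reproduce, so the check is one of logic. For one carried-over event, let:

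- P = peak grade in the parent study
- G = peak grade between the parent final visit and the first OLE dose, entry grade included
- S = grade at OLE start (the recorded initial grade), so G ≥ S
- W = worst grade on or after the first OLE dose, so W ≥ S
- M = recorded most extreme grade = max(P, G, W), from Protocol 4.4.1.1, 5.4.1 and 5.4.6.3

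The SAP 4.2.2 test is M > S. The Protocol 6.3.1 test is W > S.

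**Missed worsenings.** If W > S, then M ≥ W > S. The grade comparison therefore misses no event that worsened in the OLE.

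**False flags.** If M > S but W = S, then max(P, G) > S. The false flags are exactly the events that entered below an earlier peak and did not worsen afterwards.

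Illustrations (G = S except in the last row; every event ends after the first OLE dose):

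| Event | P | G | S | W | M | SAP: M > S | Protocol: W > S | M > P as well |
|---|---|---|---|---|---|---|---|---|
| 1 | 3 | 1 | 1 | 1 | 3 | yes | no | no |
| 2 | 3 | 1 | 1 | 2 | 3 | yes | yes | no |
| 3 | 2 | 1 | 1 | 3 | 3 | yes | yes | yes |
| 4 | 2 | 2 | 2 | 2 | 2 | no | no | no |
| 5 | 2 | 3 | 1 | 1 | 3 | yes | no | yes |

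Events 1 and 2 carry the same recorded pair (initial 1, most extreme 3), yet only event 2 worsened in the OLE. No rule using those two fields alone can separate them. The parent peak settles event 3 as worse after the parent study, but not event 2. Event 5 shows that a rise in the gap before the first OLE dose can look like worsening. That gap exists: patients leaving GA28948 or GA28949 at Week 10 start 2 to 4 weeks later (Protocol 4.1.1), and Protocol 4.4.1 provides for a Week 0 visit more than 7 days after the parent final visit.

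**Outputs reached.** The incidence and event-total tables are affected. Tables by severity are affected only if they use the recorded most extreme grade, and the SAP does not say which grade they use. The rates per 100 patient-years are not affected, because SAP 4.2.2 admits only events with onset after the first OLE dose.

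**GA27927.** Its patients may enter Part 1 (Protocol 4.1.1), and their ongoing events are reopened with the parent start date (Protocol 5.4.1). Read literally, the named list and the limiting sentence after it can exclude such an event even when it worsened in the OLE. The sentence on earlier-onset events that follows names no study, so the text can be read either way.

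**The case against.** The strongest reply is that SAP 4.2.2 already speaks of worsening and of intensity increasing. The grade comparison is worded as a necessary condition, and an event at Grade 1 throughout the OLE has not worsened. SAP 3 adds: "Summaries will primarily focus on safety events arising after first dose of study drug in Study GA28951 Part 1 (OLE"), and SAP 4.2.4 limits the timeframe to the OLE. This shows what was intended. It does not cure the rule, because the SAP explains the grade comparison as being the increase, gives no window for it and offers no other test. SAP 4.4 lists only the anti-therapeutic antibody change, so nothing suggests a deliberate departure from Protocol 6.3.1.

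It is also true that the SAP never says its initial and most extreme intensities are the eCRF grades described in the protocol. That link is an inference, but they are the only two grades that the documents describe for an event.

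Three further points stand. The study is single-arm and descriptive, with no tests and a synoptic report. Over-counting is the cautious direction for safety. And a remedy that moved every unresolved event out of the main display would hide true worsenings such as event 2, which would be worse than the over-count.

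**Conclusion.** The rule is wrong as written for carried-over events and should be corrected. It departs from Protocol 6.3.1 by leaving the worsening undated. Within the grade comparison the direction is certain: over-counting, confined to events that entered the OLE below an earlier peak and did not worsen there. The size is unknown, because the documents do not say how many events were ongoing at rollover or how many of those had improved.

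A reader might infer more than this in three ways, and the documents do not support it:

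- That the SAP's definition as a whole can only over-count. The omission of GA27927 can work in the other direction.
- That the infection and malignancy rates per patient-year are inflated. Their onset rule excludes carried-over events.
- That the overall safety profile is materially overstated. No frequency is available to show it.

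The conclusion assumes that the flag is programmed from the two recorded grades, and that sites recorded them as the protocol instructs.

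**What to change.** In SAP 4.2.2:

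1. Attach the first-OLE-dose timing to worsening as well as to new events.
2. Define a carried-over event as treatment emergent only if its worst grade on or after the first OLE dose exceeds its OLE-start grade.
3. Add GA27927 to the list of parent studies.
4. Where only the two recorded grades exist, link each event to its parent-study record by term and start date, which the protocol makes identical. Show events with onset before the OLE on a separate line with two counts: (a) all with a most extreme grade above the OLE-start grade, as an upper bound; and (b) those whose most extreme grade also exceeds the parent-study peak, labelled as worsening after the parent study. Keep unresolved events in view.

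Count (b) should not be called a strict lower bound for OLE worsening, because it can include a rise before the first OLE dose (event 5).

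The cost is SAP wording and a data merge. The merge assumes that the parent record holds a peak grade, which cannot be confirmed because the parent forms are not in the documents. Where it does not, only count (a) is available. The price in reporting is a range instead of a single count for carried-over events. No change to treatment or visits is involved.
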